Short Title	Phase II ^b Efficacy and Safety Evaluation of TC Cream in Treating Patients with Psoriasis Vulgaris.																				
Protocol Number	105883-1																				
Clinical Trial Phase	Phase II ^b																				
IND Sponsor	Psoriasis Research Institute of Guangzhou, Guangdong, China																				
Study Centers	Multi-centers: (1) (2)																				
Primary Objective	To observe the efficacy and safety of TC Cream twice daily compared to placebo over 8 weeks in subjects of US population with stable psoriasis.																				
Secondary Objectives	To evaluate the effects and improvements of TC Cream on the quality of life in subjects with psoriasis vulgaris (stable stage) based on Psoriasis Disability Index (PDI) and Dermatology Life Quality Index (DLQI); and to determine whether there is further improvement or recurrence of psoriasis after the cessation of TC Cream after 8 weeks treatment of psoriasis vulgaris of stable stage.																				
Exploratory Objectives	To investigate and summarize the curative effects and recurrence rate of TC Cream on treated psoriasis patients of US population																				
Sample Size	Total: 88 Subjects (44 for the treatment group and 44 for the control group) 
  
 Clinical centers	Stable Stage	Total	
 
 Arm 1 TC	Arm 2 Vehicle	
   
 Center 1				
 
 Center 2				
 
 Total				
  
			Clinical centers	Stable Stage		Total	Arm 1 TC	Arm 2 Vehicle	Center 1				Center 2				Total			
Clinical centers	Stable Stage		Total																		
	Arm 1 TC	Arm 2 Vehicle																			
Center 1																					
Center 2																					
Total																					
Study Population	Male or female patients of 18-70 years old of any race with psoriasis vulgaris of stable stage																				
Duration of Administration	8 weeks																				
Washout	4 weeks for any topical or systemic corticosteroids, anti-inflammatories, antibiotics, 3-months for any systemic retinoids or biologics, or any investigational treatment																				

Protocol Version: 00

period	
Duration of Study	6 months
Study Design	Multi-center, randomized, double blind (Subject, Investigator), placebo controlled, parallel assignment
Study Agent /Intervention Description	
Treatment group: TC Cream: 0.3g/cm², applied to afflicted area after cleaning the skin with warm water; twice daily (morning and evening); dosage should not exceed 25g/day
 
Control group (placebo): Vehicle of TC Cream: 0.3g/cm², applied to afflicted area after cleaning the skin with warm water; twice daily (morning and evening); dosage should not exceed 25g/day

Concomitant Medications/ Therapies	None
Safety Considerations and Monitoring of adverse events	Do not expect any side effect other than mild red pigmentation which will disappear after the drug withdrawal.
Diagnosis and Main Inclusion Criteria	
 ✓ Male or female of 18-70 years old ✓ Women of childbearing age must be using birth control strategies defined by one of the following: 1) a barrier method (condom) and 2) oral contraceptives, during the 8-weeks study period. ✓ Consistent with diagnostic criteria of psoriasis vulgaris ✓ ISGA score ≥ 2 (at least mild severity) ✓ BSA (stable stage group): $1\% \leq$ to $\leq 20\%$ 
Note: Randomized, male-female ratio should be properly taken into consideration.

Main Exclusion Criteria	
 ✓ Subjects in pregnancy, preparing for pregnancy or breast feeding ✓ History of hyperergic or photosensitivity ✓ History of complicated cardiovascular disease, cerebrovascular disease, severe primary diseases in hepatic, kidney and hematopoietic system, or patients who are diagnosed with psychotic disorders ✓ Within 2/4 weeks prior to randomization the patients have taken treatment with following approved or investigational psoriasis therapy of the target lesions: 
 ○ Topical treatments ○ PUVA, UVB or Grenz ray therapy ○ Any systemic treatments other than biologicals with a possible effect on psoriasis (e.g., corticosteroids, vitamin D analogues, retinoids, hydroxycarbamide, azathioprine, methotrexate, cyclosporine, other immunosuppressants).

	
 ○ Any types of investigational therapy for psoriasis within the last 30 days ✓ Within 3 months prior to randomization the patients have taken systemic treatment with retinoids or biological therapies (marketed or others) with a possible effect on psoriasis (e.g., alefacept, efalizumab, etanercept, infliximab). ✓ Planned initiation of, or changes to, concomitant medication that could affect psoriasis (e.g., beta blockers, anti-malaria drugs, lithium) during the double-blind phase of the study.
Endpoints	
Observation of Curative Effects:
 
 (1) Severity of local signs - Phenotypes 
 a. Induration (average over all lesions) b. Erythema (average over all lesions) c. Scaling (average over all lesions) (2) Extent - Body Surface Area (BSA) affected (3) Symptoms - Pruritus/itching (average over 24 hours) (4) Visual assessment: Digital photographs on the target skin lesion 
Note: (1) All patients will be examined and photographed before (first visit) and after (end of the curative treatment) treatment with TC Cream or placebo.
 
(2) The investigator(s) can, not must, consider enrolling the patients may have a lesion on elbow and/or knee. However, the patients who have no lesion on elbow or knee or only have a lesion on one of parts can be enrolled into this research.
 
Outcome Measures:
 
 • Primary Endpoint: 
 (1) Investigator's Static Global Assessment (ISGA) (2) Assessment of Targeted Lesions • Secondary Endpoint: 
 (1) PASI \geq 75% improvement • Tertiary Endpoint: 
 (1) Psoriasis Disability Index (PDI) (2) Dermatology Life Quality Index (DLQI) 
Statistical Analysis:
 
Comparison between two groups will be made using the t-test with two-sided 95% confidence interval (CI) for the difference in response rates between the two treatment groups (ITT, TC vs. Vehicle). A P-value < 0.05 is considered to be statistically significant.
 
Frequency of Evaluation:
 
 – 0 (before treatments), 2, 4, 6 and 8 weeks – After the initial 8 weeks of treatment, there will be a follow up period of 4 weeks during which no treatment is used.

Schematic Flow of Study Design

1. INTRODUCTION

1.1 Background

1.1.1 Study Disease: Psoriasis Vulgaris

Psoriasis is a common, genetically determined, inflammatory, and proliferative skin disease. It is a disabling disease and may even be life-threatening on rare occasions. The duration may vary from a few weeks to a whole lifetime. The clinical course is unpredictable, but in most patients, psoriasis is a chronically remitting and relapsing disease. It has significant social, psychological, and economic consequences. The impact of psoriasis on the quality of life is reported to be comparable with that observed in other chronic medical conditions such as diabetes and depression. Epidemiological studies indicate that psoriasis is associated with other serious conditions such as diabetes, heart disease, and obesity. According to the National Institutes of Health, as many as 7.5 million Americans have psoriasis. Chronic psoriasis vulgaris is the most common form of psoriasis and affects about 90% of patients with psoriasis ^[1].

Although there is currently no cure for psoriasis, there are three categories of treatment options (Topical, Phototherapy, and Systemic) ^[2] that can clear psoriasis for a period, yet each treatment has advantages and disadvantages. Ultraviolet light treatment is frequently combined with topical (e.g., coal tar, calcipotriol) or systemic (e.g., retinoids) treatment. Long-term toxicities are observed with all currently available systemic treatments^[3,4], such as teratogenic effects and the influence on lipid metabolism with retinoids, cumulative liver toxicity and the risk of bone marrow suppression and of malignancies with methotrexate, hypertension, renal dysfunction, and risk of malignancies with cyclosporine A, and increased risk of squamous-cell carcinoma and melanoma with PUVA therapy. A few new biologics have been developed to treat psoriasis; however, not only are the drug prices extremely high, but they are also often associated with severe adverse effects.

Due to the high frequency of adverse reactions to systemic and Phototherapy, topical agents are often used as first-line therapy for plaque psoriasis. These include salicylic acid, steroids, Vitamin D analogues (such as calcipotriol), tazarotene, dithranol, coal tar extracts, and a combination of any of these agents. Retinoid drugs cause a high rate of irritant reactions on the skin, and as a result, they can only be used in the stable stage of psoriasis; while hormone and immunosuppressive treatments have evident side effects, their short-term efficacy is reasonably good. Recurrence is common after withdrawal of these treatments, and the disease tends to turn into chronic, stubborn, and become more challenging to treat.

1.1.2 Study Agent: TC Cream

TC Cream is a botanical drug developed for the topical treatment of psoriasis vulgaris. It has been proven through phase II and phase III clinical trials conducted in China to have remarkable efficacy and minimal side effects, not only for patients with stable disease but also during flare. It is especially effective for first-time psoriasis patients who have never used any other treatment in the past.

The TC Cream drug product contains a well-characterized plant extract, TC, from a Chinese traditional herb, and a partially purified crystalline powder. It can be used for various skin illnesses. The activity is considered to arise from the whole mixture of the extract, not from an individual component. Drug substance and drug product specifications have two ID tests, including an HPLC method, to achieve effective treatments. So far, the three-month accelerated stability data and long-term (36 months for the drug substance and 45 months for the TC Cream) storage at room temperature have not shown any negative trends. Robust manufacturing of the drug substance and the drug product has been established with tight specifications to assure consistent quality control of the drug product.

1.2 Rationale

TC Cream has been shown to accelerate cutin reduction, reduce inflammation, prevent anaphylaxis and allergy, and exhibit notable antibacterial and anti-pruritic effects through pre-clinical studies and Phase III and Phase II safety and efficacy clinical studies in China. In addition, it can improve the pathological changes of over-proliferation and parakeratosis of epidermal cells in psoriasis.

1.3 Control Agent: Placebo

Vehicle of TC Cream with the same manufacturing formulation and process, without the drug substance added.

1.4 Route of Administration

The study agents are for external/topical use only. Apply a thin layer (0.3g/cm²) of TC Cream to the affected area(s) twice daily. Daily doses exceeding 50g have not been systematically studied.

1.5 Summary of Previous Pre-clinical Studies

[figure not shown]
1.5.1 Pharmacology

Pharmacological experiments show that TC Cream can inhibit mitosis in the vaginal epithelial cells of mice; it can increase the thickness of the granular layer in the skin scales of rat tails; it has a markedly strong inhibition of passive cutaneous anaphylaxis in

Protocol Version: 00

rats. In addition, it significantly inhibits croton oil-induced mouse ear swelling and albumin-induced rat paw edema and evidently raises the itch threshold to histamine phosphate in guinea pigs. Research shows that TC Cream promotes cutin reduction, anti-inflammation, anti-anaphylaxis, and anti-allergy effects, as well as notable antibacterial and antipruritic effects. Besides, it can improve the pathological changes of over-proliferation and parakeratosis of epidermal cells in psoriasis. It is an effective psoriasis treatment.

1.5.2 Toxicology

2. OBJECTIVES

- To observe the efficacy and safety of TC Cream twice daily compared to placebo over 8 weeks in subjects of the US population of patients with psoriasis vulgaris (stable stage) based on Investigator's Static Global Assessment (ISGA), Target Lesion, Psoriasis Area and Severity Index (PASI).
- To evaluate the effects and improvements of TC Cream on the quality of life in subjects with psoriasis vulgaris based on Psoriasis Disability Index (PDI) and Dermatology Life Quality Index (DLQI), and to determine whether there is further improvement or recurrence of psoriasis after the cessation of TC Cream after 8 weeks of treatment for psoriasis.
- To investigate and summarize the curative effect and recurrence rate of TC Cream on treated psoriasis patients of the US population.

3. STUDY DESIGNS

This is a double-blind, randomized, placebo-controlled, parallel-controlled, multi-center, phase II^b clinical trial.

This phase II^b clinical trial includes two study groups: a treatment group and a placebo

Protocol Version: 00

group, and it will be conducted at multiple centers. The total number of sample cases needed for this trial is 88 patients enrolled. The subjects are both inpatients and outpatients with BSA $\geq 1\%$ to $\leq 20\%$. Approximate time to complete study enrollment is 1~2 days. The expected duration of subject participation is 8 weeks. After the initial 8 weeks of treatment, there will be a 4-week follow-up period during which no treatment is used.

3.1 Randomization

Subjects will be randomly assigned to a treatment agent according to a predetermined computer-generated randomization scheme.

Subjects will be assigned consecutive subject numbers in ascending order. This number will identify the subject and determine the treatment of drug product administration according to the randomization scheme.

3.2 Blinding

Double blinding: the subject(s), investigator(s), monitor, and, in some cases, data analyst(s) will be blinded from the treatment agents throughout the study.

3.3 Patient Selection

3.3.1 Study Population

The study will include psoriasis patients in the US population.

3.3.2 Sample Size

A total of 88 subjects in the study centers will be included.

3.3.3 Screening Procedures

Screening procedures will include the following:

- medical history
- vital signs (blood pressure, pulse rate, respiration, and temperature)
- demographic data collection and measurements of height and weight
- photocopies of the affected skin
- physical examination.

3.3.4 Inclusion Criteria

- Age of 18-70 years old. Both men and women, and members of all races and ethnic groups, will be included
- Consistent with the diagnostic criteria of stable-stage psoriasis vulgaris, and have at least two target lesions suitable for evaluation

Protocol Version: 00

- Women of childbearing age must be using birth control strategies defined by one of the following: 1) a barrier method (condom) and 2) oral contraceptives, during the 8-week study period.
- ISGA score ≥ 2 (at least mild severity)
- BSA (stable stage group): $1\% \leq$ to $\leq 20\%$
- Signed a written informed consent document
- No additional exposure to the sun

Note: Randomized, male-female ratio should be adequately taken into consideration.

3.3.5 Exclusion Criteria

- Subjects in pregnancy, preparing for pregnancy, or breastfeeding
- History of hyperergic or photosensitivity
- History of complicated cardiovascular disease, cerebrovascular disease, severe primary diseases of hepatic, renal, and hematopoietic systems, or patients who are diagnosed with psychotic disorders
- History of photosensitive diseases such as porphyria, chronic actinic dermatitis, Xeroderma
- Within 2/4 weeks before randomization, the patients have taken treatments with the following approved or investigational psoriasis therapy of the target lesions:
 - Topical treatments
 - PUVA, UVB, or Grenz ray therapy.
 - Any systemic treatments other than biologicals with a possible effect on psoriasis (e.g., corticosteroids, vitamin D analogues, retinoids, hydroxycarbamide, azathioprine, methotrexate, cyclosporine, other immunosuppressants).
 - Any other type of investigational therapy for psoriasis
- Within 3 months before randomization, patients have received systemic retinoid or biological therapy (marketed or otherwise) that may affect psoriasis (e.g., alefacept, efalizumab, etanercept, infliximab).
- Planned initiation of, or changes to, concomitant medication that could affect psoriasis (e.g., beta blockers, anti-malaria drugs, lithium) during the double-blind phase of the study.
- The history of allergic reactions attributed to similar dermatological drugs are excluded according to specific cases decided by investigators

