3.3.6 Washout Period

- 4-weeks for any topical or systemic corticosteroids, anti-inflammatories, antibiotics,
- 3-months for any systemic retinoids or biologics, or any investigational treatment
- Only specific procedures are performed as indicated in the table of Schedules of

Events, if subjects need washout periods

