4.3 Scoring of Clinical Symptoms

4.3.1 Severity of local signs - Phenotypes

a) Induration (elevation)

The NPF induration card is to be used to assist the induration assessments.

Table 1 Induration (average over all lesions)

[figure not shown]
b) Erythema (Redness)

Table 2 Erythema (average over all lesions)

[figure not shown]
3	Moderate	reddish patchy coloration
4	Severe	bright red coloration
5	Very severe	dusky to deep red coloration

c) Scaling

Table 3 Scaling (average over all lesions)

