5.1.3 Psoriasis Area and Severity Index (PASI)

PASI is a physician-performed assessment of both the extent of psoriasis on the four body areas (head, trunk, upper limbs, and lower limbs) and the degree of plaque erythema, scaling, and thickness. The PASI score accounts for both the extent of BSA affected by erythema, scaling, and thickness, and the severity of erythema, ranging from 0 (no disease) to 72 (maximal disease).

The proportion of subjects achieving PASI 75, defined as $\geq 75\%$ improvement in PASI score from baseline at the end of 8 weeks of treatment, is the secondary efficacy endpoint

Protocol Version: 00

in this study.
(See attached PASI scoring template)

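### The short-window prior-therapy exclusion is worded for the target lesions only, so recent light therapy or non-steroid topicals on other plaques can be present at baseline in the ISGA primary and PASI 75

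*Combined protocol and SAP*

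**What the plan says.** **Exclusion.** Section 3.3.5 opens its short-window criterion with "Within 2/4 weeks before randomization" and applies it where "the patients have taken treatments with the following approved or investigational psoriasis therapy of the target lesions". The listed therapies are topical treatments, "PUVA, UVB, or Grenz ray therapy", non-biological systemic treatments and investigational therapy. The synopsis (Main Exclusion Criteria) carries the same limit: "the patients have taken treatment with following approved or investigational psoriasis therapy of the target lesions". A separate criterion in 3.3.5 has no lesion limit: "Within 3 months before randomization, patients have received systemic retinoid or biological therapy (marketed or otherwise) that may affect psoriasis".

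**Washout.** Section 3.3.6, repeated in the synopsis, also has no lesion limit. It requires "4-weeks for any topical or systemic corticosteroids, anti-inflammatories, antibiotics", and 3 months for systemic retinoids, biologics or investigational treatment.

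**What is scored.** Section 5.1 names two primaries, ISGA and the target-lesion assessment.
- ISGA (5.1.1, Table 6) is anchored to the majority of lesions.
- The sign scores in 4.3.1 are whole-patient averages, for example "Induration (average over all lesions)".
- PASI (5.1.3), the basis of the secondary endpoint, rates "the extent of psoriasis on the four body areas (head, trunk, upper limbs, and lower limbs)".
- Only the target-lesion primary (5.1.2) is confined to two pre-selected plaques.

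**The concern.** The exclusion is matched to one primary endpoint and not to the other. A patient with two untreated plaques suitable as target lesions, and other plaques treated until shortly before randomisation, satisfies the wording of 3.3.5. If the treatment belongs to a class that 3.3.6 does not name, nothing else in the visible text keeps that patient out.

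The baseline for ISGA and PASI is then taken on partly treated skin, and the earlier treatment stops at about the same time. Section 5.2 lets baseline scoring fall up to a week before treatment, and the synopsis allows no concomitant therapy.

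Because ISGA success is a change of at least two grades from baseline, a shifted baseline alters what the patient must achieve. The target-lesion primary is not exposed in the same way, so the two primaries could disagree for a reason unrelated to the drug.

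**Working it through.** **Step 1. Which therapies escape both rules when used only on non-target lesions?**

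| Prior therapy | 3.3.5 short window | Rules without a lesion limit | Gap? |
|---|---|---|---|
| Topical corticosteroids, anti-inflammatories, antibiotics | Target lesions only | 4 weeks (3.3.6) | No |
| Systemic retinoids, biologics | Own 3-month criterion | 3 months (3.3.5 and 3.3.6) | No |
| Investigational treatment | Target lesions only | 3 months (3.3.6) | No |
| Other systemic treatments | Worded for target lesions, but the drug reaches all lesions | Corticosteroids, anti-inflammatories and antibiotics named | Not readily |
| Light therapy (PUVA, UVB, Grenz ray) | Target lesions only | Not named | Yes, if confined to other plaques |
| Vitamin D analogues, tazarotene, dithranol, coal tar, salicylic acid as topicals | Target lesions only | Not named | Yes, unless a site reads them as anti-inflammatories |

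The topicals in the last row are those that section 1.1.1 lists, with steroids, among agents often used first-line.

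**Step 2. What does a shifted baseline do to ISGA success?** Section 5.1.1 defines success as baseline minus follow-up of at least 2, with entry allowed at ISGA 2.
- Baseline 3: follow-up must be at most 3 - 2 = 1, so 0 or 1 succeeds.
- Baseline 2: follow-up must be at most 2 - 2 = 0, so only 0 succeeds.

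Adding the clear or almost-clear condition of section 5.1 changes neither line. A patient whose underlying grade is 3 but who is scored 2 because of earlier therapy therefore faces the stricter requirement.

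**Step 3. Could it cost power?** The plan's own figure is 88 patients (44 per arm) at 90% one-sided (9.1). It cannot be reproduced, because no response rates, effect size or alpha are given with it. The following is an illustration on assumed rates.

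Power = Phi[(d - 1.96 x se0) / se1], where d is the difference in response rates, se0 the pooled and se1 the unpooled standard error, with 44 per arm and two-sided 0.05 (the level in 9.2.4). Vehicle 10% and TC 39.1% give 90%. Let a share f of patients show no treatment difference because of earlier therapy.

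| f | They respond at the vehicle rate | They respond at the TC rate in both arms | They cannot respond in either arm |
|---|---|---|---|
| 0 | 90% | 90% | 90% |
| 10% | 84% | 81% | 85% |
| 20% | 76% | 69% | 80% |
| 30% | 67% | 56% | 72% |

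Worked cell (f = 20%, vehicle rate):
- TC rate = 0.10 + 0.291 x 0.8 = 0.3328, so d = 0.2328.
- Mean rate = (0.3328 + 0.10) / 2 = 0.2164.
- se0 = sqrt(0.2164 x 0.7836 x 2/44) = 0.0878.
- se1 = sqrt((0.3328 x 0.6672 + 0.10 x 0.90) / 44) = 0.0842.
- Power = Phi[(0.2328 - 0.1721) / 0.0842] = Phi(0.72) = 76%.

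The rates, f and the premise that affected patients show no treatment difference are all assumptions. The table shows that a modest share could matter at 44 per arm; it does not estimate the loss in this trial.

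**The case against.** **The washout already does most of the work.** It has no lesion limit and covers topical corticosteroids, anti-inflammatories, antibiotics and investigational treatment. A reader might infer that anyone recently treated outside the target lesions enters with carry-over. The documents do not support that; this objection stands, and it limits the point to the last two rows of the table in step 1.

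**The phrase may not be meant as a strict lesion limit.** The list beneath it includes systemic treatments, which cannot be confined to two plaques. A site might therefore apply it to the whole patient, or might treat the non-steroid topicals as anti-inflammatories. Both readings are possible. That leaves eligibility to each site's reading, which is a reason to settle the wording.

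**Few patients may be affected.** ISGA follows the majority of lesions, so treating a few plaques need not move the grade. Section 5.1.2 also asks for target lesions that represent the disease, which makes two untreated plaques among mostly treated ones a doubtful choice. Both features limit the share affected, but neither makes it zero.

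**The direction is uncertain.** A reader might infer bias towards TC Cream, or a difference that is always diluted. Neither follows. Assignment is randomised and blinded (3.1, 3.2), so carry-over is balanced in expectation. Study cream goes on all affected skin (3.4.1), so plaques that worsen after earlier therapy stops receive TC or vehicle; if TC works, the contrast could even widen. The remark in 1.1.1 that recurrence is common after withdrawal is only indirect support, because it is not specific to the therapies left in the gap.

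**The Schedule of Events is not shown.** Section 3.3.6 refers to it for washout procedures, so its content on this point is unknown.

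**Conclusion.** The point holds in a limited form. The lesion scope of the short-window exclusion is narrower than that of the ISGA primary and PASI 75, and the washout does not close the gap for light therapy or for non-steroid topicals used on non-target lesions. Patients so treated can be enrolled; the documents do not show that they will be, or how many.

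The consequence supported by the text is a baseline ISGA and PASI that may reflect earlier therapy. On ISGA, a one-grade shift from 3 to 2 tightens success from 0 or 1 to 0 only. The risk is added noise or lost power on ISGA and PASI 75, chance imbalance at 88 patients, and possible disagreement between the primaries. No systematic advantage to either arm is expected. The size is unknown, and the power figures above hold only under their stated assumptions.

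This should be corrected before enrolment. Section 9.2.4 plans an unadjusted comparison of response rates, and the screening list in 3.3.3 does not ask which plaques were treated, so the analysis as planned would not remove the effect.

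**What to change.** Reconcile 3.3.5, 3.3.6 and the synopsis on two matters.

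1. **Lesion scope.** Make the prior-therapy exclusion cover the lesions that ISGA and PASI score. The shortest route is to remove the target-lesion limit in 3.3.5 and in the synopsis. Section 3.3.6 needs no change on this matter.
2. **Therapy classes.** Make the exclusion and the washout name the same classes, and state explicitly where light therapy and the non-steroid topicals belong.

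The windows also disagree. The 2/4-week window is not assigned to individual therapies, 3.3.6 gives 4 weeks for its named classes, and for investigational therapy the synopsis gives both 30 days and 3 months. These must be reconciled in the same edit; the sponsor sets the windows.

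The cost is a four-word deletion in two places and an aligned list of classes. The downside is that a few candidates may need a washout or become ineligible.
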